5.0 Inclusion and Exclusion Criteria/ Study Population

Inclusion Criteria for Adolescents:

- Participants in this study will be youths aged 14-17 with a documented history of ASD who are enrolling in a PEERS program at MUSC.
- Participants will be screened for eligibility using the ADOS-2, the gold standard instrument for diagnosing ASD. A score falling within the autism spectrum range on the ADOS-2 is required.
- Participants will also be screened for IQ using the K-BIT2, an IQ measure appropriate for children and adolescents. Subjects must score higher than 70 on the K-BIT2.
- Participants must be willing to enroll in PEERS training and to receive brain stimulation prior to being included in this study

Exclusion Criteria for Adolescents:

- Epilepsy, or a seizure in the last year
- Vagal nerve stimulators
- Participants may continue to take prescribed medications during the course of the treatment. However, no dosage or agent changes may be made one month prior to the study or during the study. If a medical or behavioral treatment change must be made during the course of the study, participation will be discontinued.
- Allergy to benzocaine
- Prior brain stimulation (tDCS, TMS, ECT, DBS) intervention
- Inability or unwillingness of subject or legal guardian/representative to give informed consent
- Non-native English speaker
- Metal pins, plates or clips in the body or orthodontics
- Surgical implants such as pacemakers or cochlear implants
- Permanent makeup or tattoos near the face or head
- Metal fragments in the body (from welding, shrapnel, BB guns) or suspect that they have fragments
- Claustrophobia
- Past closed head injury or concussion
- Currently under the influence of alcohol or other recreational drugs
- Smoker
- Cannot understand the fMRI task instructions
- Cannot lay still in the mock scanner for a period of 5 minutes
- Prior PEERS training

Inclusion Criteria for Parents:

- Have a child with Autism Spectrum Disorder and willingness and ability to participate in the weekly PEERS session

Exclusion Criteria for Parents:

- Enrolled in an academic course in which Drs. [name], [name], [name] or [name] are instructors

No individual will be excluded based on race, gender, or ethnicity. The parent can be either male or female.

Only adolescents from age 12-17 will be included because the study is focused on behavioral and neurostimulation interventions that are expected to enhance social skills. Adolescence is a developmental time period where social information processing is particularly relevant.

6.0 Number of Subjects

A total of 34 subjects will be recruited for the study (17 adolescents and their parent), but a drop-out rate of approximately 40% is expected, leaving 10 adolescent subjects with complete datasets.

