10.0 Study Design / Methods

We will conduct brain stimulation with 17 randomized adolescent participants at initial enrollment. Drop-outs are expected, with the goal of having 10 youths with ASD complete the study, with the same number of parents actively participating by the end of the experiment.

The following table summarizes the schedule of activities for a subject:

Schedule of events	Activities	Time commitment for volunteer	Compensation
Initial visit with research coordinator, Drs. [name] and [name]	Consent (parent and child)	15 min	\$25 (child) \$15 (parent)
	Medical & MRI screening (parent and child)	5 min	
	ADOS-2 & KBIT-2 (with child), clinical measures (with parent)	90 min	

	Mock scanner training with child	10-15 min	
	fMRI scanning with child	30 min	
	tDCS acclimation with child	10 min	
PEERS weekly sessions	PEERS training plus active / sham tDCS	1 hr / week x 14 weeks	\$15 per session (child) \$0 (parent)
Post-intervention visit	clinical measures (with parent), fMRI scanning (with child)	45 minutes	\$25 (child) \$25 (parent)
14-week follow-up visit	clinical measures completed online (by parent)	30 minutes	\$10 (child) \$50 (parent)

Parents will make initial phone or email contact with the study coordinator. The study coordinator will conduct a brief telephone screening to determine preliminary eligibility for the study. If eligible, the study coordinator will schedule the initial visit.

The initial visit will last approximately 3 hours. Following informed consent (see Section 9.0), an in-depth MRI screening form will be filled out by the parent and the medical history information obtained during the initial telephone interview will be reconfirmed. Any female participants will complete a pregnancy test. [name] will then conduct the ADOS and K-BIT with the child while the parent completes the following clinical outcome measures on a computer (using RedCap) in a separate room: Social Responsiveness Scale-2 [26], the Social Skills Improvement System, the Quality of Play Questionnaire, the Aberrant Behavior Checklist, and the Test of Adolescent Social Skills Knowledge-Revised [27]. The child and parent are given a 10-minute break and a healthy snack, if desired.

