A brief questionnaire about adverse effects will be completed with participants and their parents immediately following the second and last treatment sessions. Tolerance for tDCS will be monitored during tDCS delivery by noting the frequency with which a subject reported irritation, discomfort, burning or pain, whether a subject attempted to remove the tDCS leads, whether a subject wished to discontinue the procedures due to the tDCS (rather than the PEERS training). After the second and last PEERS sessions, the experimenters will administer a brief questionnaire with the subject about whether they felt uncomfortable itching, tingling, burning during the session or whether they have had headaches, neck pain, sleepiness, moodiness in the past week. Any of these effects will be recorded. We will conclude that tDCS can be tolerated if these effects are experienced less than 25% of the time for a given individual. We will also report on how many subjects tolerated the procedures.

The child and parent receive compensation in the form of gift cards following each visit to MUSC (see Table above).

After 14-weeks of PEERS training, subjects will return for a post-treatment session in which the clinical outcome measures will be completed by parents and fMRI session will be completed by the participants (same procedures as before excluding tDCS acclimation).

Finally, 14 weeks after the post-treatment session, the parent will be sent a reminder via RedCap to complete the clinical outcome measures. In addition, both parent and child will be asked to guess which condition the child was assigned to (active or sham tDCS). Once the final follow-up surveys are completed in RedCap, the final gift card of \$75 is mailed to the family.

Information about which condition a subject was assigned to is not typically provided, but if a subject asks, we can tell them after all study procedures are completed and the blind is lifted. Study personnel will also be asked to guess the condition before the study blind is lifted.

Source records: the data collected from subjects include: parental and subject responses on clinical tests and questionnaires, anatomical and functional MRI scans, reaction time and accuracy responses on the fMRI task.

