This project involves both a medical device intervention (tDCS) and a behavioral intervention (PEERS training). fMRI scanning, while not an intervention, will be conducted prior to and following 14-weeks of weekly tDCS sessions.

For tDCS, safety of the participants will be monitored during and immediately after delivery of tDCS to the scalp. During tDCS stimulation, subjects have the option of wearing a ski cap which may reduce discomfort. They will be introduced to the ski cap during the tDCS acclimation session on the initial visit. Some subjects may opt not to wear the ski cap, but it will not affect tDCS delivery. At the end of the sessions that involved tDCS delivery, subjects will be asked if they felt or feel any sensations on the scalp where the electrode was and responses are recorded by the experimenter. In [name] experience and other reports in the literature, any sensations of pain, tingling, itching, stinging or irritation follow the onset of stimulation for about 30-60 seconds and do not persist longer than that. If subjects report feelings of sensation or pain that are unmanageable, a local analgesic cream (benzocaine) can be used or the level of current can be reduced to help them complete the session. [name] will be present during all experimental sessions when tDCS is delivered and will be able to monitor for any adverse medical effects.

Adverse effects will be defined by painful sensations that are unmanageable and cannot be alleviated using the procedures outlined above or by persistent reports of high levels of pain by a participant. Although we do not expect this to occur, such events will be reported to the IRB.

For PEERS training, which is a behavioral intervention, the risks are minimal, but include potential discomfort in interacting with other individuals. Should this intervention prove to be too distressful for an individual, the individual will have the option to discontinue the study. Distress would be indicated by persistent withdrawal from or refusal to engage in PEERS activity, persistent protesting, crying or agitation during PEERS sessions. [name] and the research assistant will make the decision as to whether an individual is experiencing distress. When these behaviors lead to removal from the study, these will be reported as adverse events to the IRB.

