14.0 Withdrawal of Subjects (if applicable)

Subjects can withdraw from the study voluntarily. Although financial incentives will be provided for continued participation, subjects are not forced or otherwise coerced to participate.

The investigators may withdraw an individual from the study for the following reasons: (a) participant does not understand or follow instructions, (b) participant is not cooperative or is disruptive during PEERS/ tDCS delivery or fMRI scanning sessions, (c) the safety of the individual is at risk due to tDCS

delivery, as described above (persistent or intense experience of pain), (d) the subject exhibits severe psychological distress or anxiety during tDCS delivery, PEERS activities or fMRI scanning. If any of these reasons leads to withdrawal from the study, Drs. [name] / [name] would discuss the reason(s) with the child and parent as soon as possible following the incident. This could be immediate if only the volunteer would be affected (e.g., during fMRI scanning), but if there are disruptions or a failure to follow instructions during a PEERS session (which takes place in a group format), [name] will discuss the issue with the parents following the session.

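### The protocol, as available, has no route to the parent-completed primary measures after an adolescent leaves early, so the active-sham comparison would in effect be among completers

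*Combined protocol and SAP*

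**What the plan says.** Section 6.0 recruits 17 adolescents, each with a parent, and states that "a drop-out rate of approximately 40% is expected, leaving 10 adolescent subjects with complete datasets". Section 10.0 says that the 17 are randomised, half to active and half to sham tDCS, and sets a goal of 10 completing, "with the same number of parents actively participating by the end of the experiment".

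Section 4.0 defines the primary endpoints as pre-to-post changes on five clinical measures, and Section 10.0 has the parent complete all five in RedCap at baseline. After 14 weeks of PEERS, "subjects will return for a post-treatment session in which the clinical outcome measures will be completed by parents". Then, "14 weeks after the post-treatment session, the parent will be sent a reminder via RedCap to complete the clinical outcome measures".

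Exit is covered in three places:

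- Section 5.0: "If a medical or behavioral treatment change must be made during the course of the study, participation will be discontinued".
- Section 13.0 lets an adolescent discontinue if PEERS is too distressing and, on distress behaviours, adds: "When these behaviors lead to removal from the study, these will be reported as adverse events to the IRB".
- Section 14.0 allows voluntary withdrawal and continues: "The investigators may withdraw an individual from the study for the following reasons". The reasons listed include failure to follow instructions, disruption, pain from tDCS and severe distress.

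None of the three mentions further outcome collection. For the analysis, Section 4.0 names non-parametric tests and Section 12.0 names descriptive statistics. Neither defines an analysis set or says how missing scores are handled.

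**The concern.** Both later assessments depend on the adolescent reaching the end of PEERS and the family returning. Someone who stops in week 5, for example, has no post-treatment visit, and so no date from which the online follow-up could be counted. A score not collected when due cannot be recovered later.

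The plan itself expects about 40% to drop out. If their scores are missing, active and sham are compared only among those who stayed, and randomisation does not fully protect that comparison. If leaving is related to how the adolescent is changing, and the arms differ in how many leave or in how strong that relation is, the difference between arms is shifted. This applies equally to a test and to a table of means, so it does not matter here which of Sections 4.0 and 12.0 governs.

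**Working it through.** **The plan's own figure.** 17 × (1 − 0.40) = 10.2, so 10 completers; in reverse, 10 / 0.60 = 16.7, so 17. The figures agree. The implied loss is 17 − 10 = 7, and 7/17 = 41%.

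**Is there a trigger after exit?** The places where one could sit are:

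| Section | Content | Collection after exit? |
|---|---|---|
| 5.0 | Treatment change ends participation | Not mentioned |
| 9.0 | Protesting child is encouraged to come back for sessions | No; concerns attendance |
| 10.0 | Post-treatment set at a return visit; follow-up timed from it | No trigger without the visit |
| 13.0 | Discontinuation for distress; IRB report | Not mentioned |
| 14.0 | Reasons for withdrawal; discussion with family | Not mentioned |

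**Precision.** With a common SD of 1, the standard error of the difference is √(1/n₁ + 1/n₂). The splits below are assumed, except that 17 must divide 8 v 9 under equal allocation.

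- Completers, 5 v 5: 0.632
- Four of seven recovered, 7 v 7: 0.535
- All 17, 8 v 9: 0.486

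**Bias among completers.** Assume no true effect and a normal selection model. For an arm losing a proportion p, with correlation r between drop-out tendency and change, the completers' mean shifts by r × λ(p), where λ(p) = φ(z_p)/(1 − p). The bias is the difference between the arms' shifts. The documents supply none of the correlations or loss splits.

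- r = 0 in both arms: 0, however unequal the losses.
- Equal losses and equal r: 0. It is also 0 whenever the two products r × λ(p) match.
- 40% lost in each arm, λ = 0.644: (0.5 − 0.3) × 0.644 = 0.13 SD. With r = 0.3 to 0.5 in one arm only, 0.19 to 0.32 SD.
- Same r (0.3 to 0.5), losses of 3/8 v 4/9: 0.03 to 0.05 SD.
- Same r (0.3 to 0.5), losses of 5/8 v 2/9: 0.19 to 0.31 SD.
- 5/8 lost with r = 0.5, against r = 0 in the other arm: 0.51 SD.

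**Does partial recovery reduce bias?** Not necessarily. Going from 5 v 5 to 7 v 7 changes the losses from 3/8 v 4/9 to 1/8 v 2/9. With the same r of 0.3 to 0.5 in both arms, the bias moves from 0.031–0.052 to 0.044–0.074 SD, a small rise.

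**Dilution.** Suppose recovered adolescents in the active arm keep a fraction f of the effect. At 7 v 7, effect over standard error, relative to completers only, is ((5 + 2f)/7) / (0.535/0.632). This is 0.85 at f = 0, 1.01 at f = 0.5 and 1.18 at f = 1. Break-even is f = 0.46. With all 17, break-even is f = 0.38 if the active arm has 8, or f = 0.48 if it has 9.

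**The case against.** The strongest reply has four parts.

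- This is a pilot whose data analysis plan is descriptive, and every bias figure rests on assumed correlations. That stands, and it is why the point is an improvement and not a fatal flaw.
- The plan does support retention. Section 9.0 treats a refused session as a missed session, not an exit, and encourages return. Section 14.0 mentions financial incentives, and the parent's largest payment in the Section 10.0 schedule ($50) is for the online follow-up. These may lower drop-out, but they do not provide for collection once someone has left.
- The target of 10 completers suggests a completer analysis, which is a legitimate choice. A reader might infer that the plan has specified one. It has not: Sections 6.0 and 10.0 give a recruitment expectation and a goal, not an analysis set.
- The consent form was not available and may cover contact after withdrawal. It may, but permission alone would supply neither an assessment date nor an analysis set.

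A reader might also infer that the expected losses come from the exit rules in Sections 5.0, 13.0 and 14.0. The documents give no reasons for the 40%, so the outcome-related share could be anything from 0 to 7 of the 7. Nor does the plan ignore exit information: Section 10.0 notes whether a subject wished to stop because of tDCS, and removals for distress go to the IRB. What is missing is a tabulation by arm.

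**Conclusion.** The omission holds on the text available. Following the plan as written, up to 7 of 17 randomised adolescents could lack the primary outcomes, and the active-sham comparison would in effect be one of completers. Seven is an upper bound on missing questionnaires under the stated expectation, because a complete dataset may also require the scans.

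The size of any bias cannot be stated. A reader might take the illustrative values as a range for this trial, but they are neither a floor nor a ceiling: zero is possible in several ways, and more than 0.5 SD is possible under patterns chosen to be unequal. For scale, 0.51 SD is still below the completer standard error of 0.63 SD. A reader might also infer that any further collection must reduce bias. It need not if recovery is partial, and partly treated adolescents may dilute the difference.

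Full collection would remove selection by drop-out from the parent-reported comparison and bring the standard error down to 0.49 SD. That justifies a cheap change, optional in a pilot of this size.

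**What to change.** - **Sections 5.0 and 14.0:** separate stopping the intervention from stopping follow-up. The stopping rules themselves are for the sponsor and need not change.
- **Section 10.0:** unless consent is withdrawn, send the parent the RedCap measures at the scheduled post-treatment time and again 14 weeks later. Where there is no post-treatment visit, count both dates from enrolment or the first session. Record any treatment change and its date.
- **Section 12.0:** summarise the parent-reported measures by assigned arm for all randomised adolescents with post-baseline data, and show completers alongside. Tabulate drop-out and its reasons by arm, using the tolerability and distress records already planned. The fMRI and reaction-time endpoints stay limited to those scanned.
- **Consent form:** check that it permits this contact.

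The cost is protocol wording, possibly consent wording, and at most 7 × 2 = 14 extra questionnaire sets. At the parent rates in the Section 10.0 schedule that is 7 × ($25 + $50) = $525. If the $75 final card in the Section 10.0 text applies, it is 7 × ($25 + $75) = $700. Families who leave may decline, so recovery could be anywhere from 0 to 7. Showing completers alongside lets the reader see any dilution.

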7.0 Setting

- The initial visit to MUSC will take place at the Center for Biomedical Imaging (CBI) at [name]. Baseline assessments using ADOS-2 and K-BIT2 and tDCS acclimation will take place in a quiet testing room in the CBI facility. Parents will fill out questionnaires in an adjacent area at CBI. These questionnaires will be entered into RedCap and no identifying information will be linked to the survey responses.
- tDCS acclimation, Mock scanner training, and fMRI scanning will also take place at CBI.
- Brain stimulation with active or sham tDCS will take place in the MUSC Institute of Psychiatry South, 5th Floor

8.0 Recruitment Methods

- Recruitment will occur during the first 3 months of the study. Potential subjects will be recruited through the Department of Psychiatry at MUSC and from the greater Charleston area community.
- Potential subjects will be recruited through a variety of online avenues and local autism community groups and organizations, as well as advertising to the general public.
- Project Rex is an autism-focused program directed by [name] at MUSC, and has a robust social media network, a website with significant traffic, and a large patient directory. Information regarding the study and digital copies of fliers will be posted on social media forums (Facebook, Twitter, Instagram) under existing Project Rex accounts, as well as sent via email to the Project Rex mailing directory. [name] may discuss the study with patients they are actively treating as well as their family members. The study may also be advertised at any other groups, projects, or events that are being run conducted Project Rex.
- In addition to Project Rex, investigators will reach out to other local autism organizations and groups such as the Lowcountry Autism Foundation (LAF), the Lowcountry Autism Consortium, South Carolina Autism Society to provide information regarding the study to their members, as well as digital and/or physical copies of fliers to distribute to their members if they are willing to do so. Investigators will also offer to come to speak about the study and answer questions during group meetings in person for any groups who are interested. Emails will be distributed by the investigators to families and stakeholders on the Project Rex newsletter distribution list and the MUSC broadcast email system.
- Flyers will also be posted around the MUSC campus and hospital once approved.
- Investigators will reach out to local psychiatry offices and provide them with information regarding the study and digital and/or physical copies of fliers for them to share with their patients at their discretion.

- Flyers will be given to the parents of children who are enrolled in PEERS. Flyers and posters will contain information including a basic explanation of the study (investigating the use of non-invasive brain stimulation for enhancement of learning social skills in autism), eligibility (age range, diagnosis of ASD), information about financial compensation and ability to receive behavioral intervention at no cost to patient. They will also include study site and contact information for study coordinator(s).

9.0 Consent Process

Consent will take place at the Center for Biomedical Imaging at [name] on the campus of MUSC. The research coordinator will explain study procedures to the parent (or authorized legal guardian) and adolescent with ASD. Pictorial descriptions will be provided along with verbal descriptions, which is a well-accepted practice when describing research study procedures to individuals with ASD. During the consent process, the investigator will make clear that different activities will be completed by the parent and the child. To assess level of interest from youth with ASD, the coordinator will ask the parent or child volunteer if he or she has any questions about the study procedures. Following this, the coordinator will directly ask the child if he or she wants to participate. A verbal indication of "yes" or nodding of the head will be taken as assent. The child will be asked to provide their signature on an assent form. Parents will provide written consent. If either the child or parent fails to provide assent or consent, the child will not participate and will not be enrolled in the study. The parent will provide written consent for their participation. There will be no waiting period between informing the prospective subject and obtaining the consent.

The oldest adolescent participants will be 17 years of age upon enrollment. If a volunteer turns 18 during the course of the study, they will be reconsented as an adult at the next visit following their 18th birthday. Decision capacity will not need to be determined at this point because all participants will have scored in the normal range for IQ as part of the inclusion criteria.

During the study, continued assent/consent from the ASD volunteers will be indicated by willingness to participate in the PEERS group intervention, willingness to wear the tDCS electrodes, and willingness to enter the MRI scanner. Verbal or non-verbal protests for any of these procedures will indicate unwillingness to participate. However, additional attempts will be made to encourage participation within the same session. If the child continues to protest or becomes agitated, uncomfortable or non-responsive to experimenter instructions, the procedures will not be continued for that session. The child is encouraged to return for additional sessions, but will not be forced to do so.

